3.3 SAFETY ANALYSES

Safety analysis population includes all patients who are enrolled.

3.3.1 Adverse events

Adverse events are those with start date beyond or equal to the date of first administration of Obinutuzumab and until 185 days after the last Obinutuzumab dose intake or until starting a new anti-cancer therapy (whichever occurs first). After this period AEs that are believed to be related to prior study drug treatment will be collected.

All adverse events will be assigned to a Preferred Term (PT) and will be classified by primary System Organ Class (SOC) according to the MedDRA thesaurus version 22 or higher. Summary statistical tables including frequency counts and percentages and the number of adverse events will be produced.

Data will be listed by study site, patient number, and study day. Events occurring on or after treatment on Day 1 (treatment-emergent adverse events - TEAEs) will be summarized by mapped term, appropriate thesaurus levels, and NCI CTCAE v5.0 grade. In addition, SAEs, including deaths, will be listed separately and summarized.

AEs leading to treatment discontinuation will be listed.

Infusion related reactions (IRRs) and adverse events of special interest (AESI) will be summarized by descriptive statistics and will be listed.

3.3.2 Laboratory and vital signs

Relevant laboratory and vital signs (*Systolic and diastolic blood pressure, Heart rate, Body temperature*) data will be displayed by time.

Additionally, all laboratory data will be summarized by grade with use of NCI CTCAE v5.0.

For each parameter the change from baseline to each post-baseline visit will be calculated.

All medications reported will be coded using the WHO-DRL Dictionary version 2018 or higher and classified according to 3rd level ATC level subgroup and Preferred Term.

The following vital signs, when performed as per clinical practice, will be captured in the eCRF:

- Systolic and diastolic blood pressure (mmHg)

- Heart rate (bpm)
- Body temperature (°C)

For each variable the change from baseline to each post-baseline visit will be calculated.

3.4 SENSITIVITY ANALYSES

No sensitivity analyses are planned.

3.5 OTHER ANALYSES

All exploratory endpoints will be analyzed using descriptive statistics only.

In particular, the following other analyses will be performed:

Use of Obinutuzumab in real world setting

Descriptive statistics for the use of Obinutuzumab in the real world setting will be performed.

At least the following conditions will be considered in the analysis:

- Not performing obinutuzumab administration on Day 8 and Day 15 in Cycle 1 (without safety reasons)
- Maintenance period: administration of obinutuzumab in an interval superior to 10 days from the expected date (every 2 months per label). NOTE: An analysis will be performed to assess if this condition will have impact on efficacy parameters (PFS/ POD24) and to explore the delay reason (COVID-19 or others)
- All the chemotherapy scheme used with Obinutuzumab in real world setting

Prescription profile

Obinutuzumab prescription profile and chemotherapy backbone choice by Italian region, age range, patient's profile and site dimension (outlying sites/universities, etc.)

Impact of COVID-19

The COVID-19 impact will be evaluated in terms of:

- Safety (infections and COVID-19 related events)
- Maintenance delay or interruption due to pandemic status
- Therapy interruption due to patient's complications caused by COVID-19

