Synopsis Table 1. Follicular lymphoma: Obinutuzumab dose to be administered during induction and maintenance treatments (according to SmPc)

Cycle	Treatment day	Dose of Obinutuzumab
Cycle 1	Day 1	1000 mg
	Day 8	1000 mg
	Day 15	1000 mg
Cycles 2–6 or 2–8	Day 1	1000 mg
Maintenance	Every 2 months for 2 years or until disease progression (what occurs earlier)	1000 mg

Obinutuzumab will not be provided by the Marketing Authorization Holder (MAH)/sponsor for the study as this could influence the intended real-world use, and should instead follow local prescribing regulations and sourcing.

Variables

Only variables, obtained according to routine clinical practice and follow objectives can and should be documented in this study.

Primary Effectiveness Variable

- Progression of disease at 2 years (POD24), defined as the time from the date of treatment initiation with Obinutuzumab until the first documented progression of disease or death due to disease progression, whichever occurs first, within 24 months from the start of treatment with Obinutuzumab. Patients who have no disease progression and have not died due to disease progression or who are lost to follow-up at the time of analysis will be censored at the date of last tumor assessment where no progression was documented or the last date of follow-up for disease, whichever is last. Patients without post-baseline tumor assessments will be censored at the time of their baseline visit unless death due to disease progression occurs prior to their first scheduled tumor assessment. Patients who die for reasons not related to the disease progression within 24 months from the treatment start with Obinutuzumab will be excluded from the statistical analysis of the endpoint.

Moreover, the POD24 will be also analyzed as binary variable. Number and percentage of patients with its 95% confidence interval for POD24 will be calculated.

Secondary Effectiveness Variables

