2. STUDY DESIGN

2.1 DESCRIPTION OF STUDY DESIGN

This is a retrospective and prospective primary data collection and secondary data use, non-interventional, multi-center, national (involving approximately 50 Italian centers) study.

Patients should be included after the start of treatment with Obinutuzumab and chemotherapy, including newly diagnosed FL patients. Patients included should have performed at least 2 cycles of induction treatment with Obinutuzumab and chemotherapy within 1 year from beginning of treatment and will be followed up 3.5 years from the start of treatment.

For each patient, the study will consist of a period of 42 months which can include:

- an induction treatment period (approximately 6 months) in which patients will receive Obinutuzumab and chemotherapy;
- a maintenance treatment period (approximately 24 months) in which patients will receive Obinutuzumab monotherapy;
- a follow-up period of one year, after the last Obinutuzumab administration, or up to 3.5 years after start of the treatment for early discontinued patients.

A schedule of activities is provided in Appendix 1.

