2.3 PRIMARY OUTCOME MEASURES

Progression of disease at 2 years (POD24), defined as the time from the date of treatment initiation with Obinutuzumab until the first documented progression of disease

or death due to disease progression, whichever occurs first, within 24 months from the start of treatment with Obinutuzumab. Patients who have no disease progression and have not died due to disease progression or who are lost to follow-up at the time of analysis will be censored at the date of last tumor assessment where no progression was documented or the last date of follow-up for disease, whichever is last. Patients without post-baseline tumor assessments will be censored at the time of their baseline visit unless death due to disease progression occurs prior to their first scheduled tumor assessment. Patients who die for reasons not related to the disease progression within 24 months from the treatment start with Obinutuzumab will be excluded from the statistical analysis of the endpoint.

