2.4 SECONDARY OUTCOME MEASURES

2.4.1 Secondary Effectiveness Outcome Measures

- Progression free survival (PFS) at 2 and 3 years, defined as the time from the date of treatment initiation until the first documented progression of disease measured by routine clinical care or death from any cause, whichever occurs first. Patients who have no disease progression and have not died or who are lost to follow-up at the time of analysis will be censored at the date of last tumor assessment where no progression was documented or the last date of follow-up for disease, whichever is last. Patients without post-baseline tumor assessments will be censored at the time of their baseline visit unless death occurs prior to their first scheduled tumor assessment;
- Time to next treatment (TTNT), defined as the Time to initiation of subsequent systemic anti-cancer therapy following initiation of Obinutuzumab containing therapy. Patients not starting a subsequent systemic anti-cancer therapy will be censored at the date of the last study visit;
- Overall survival (OS), defined as the time from initiation of study treatment to death from any cause. Patients who still alive at the time of analysis and patients who are lost to follow-up will be censored at their last time known to be alive;
- Correlation between POD24 and OS;
- TTLCB, defined as the time from first dose to loss of clinical benefit as assessed by the treating physician (single or multiple reasons possible: e.g. disease progression, deterioration in ECOG PS, death, other). Patients who do not loss clinical benefit will be censored at the date of the last study visit. Patients without post-baseline tumor assessments will be censored at the time of their baseline visit unless death occurs prior to their first scheduled tumor assessment;
- Overall response rate (ORR);
- Complete response (CR);
- Complete response at 30 months (CR30);

- Duration of response (DoR) measured per clinical practice, defined as the time from first documentation of CR or partial response (PR) (whichever occurs first) until disease progression, as evaluated by the physician according to routine clinical practice or death. Patients who have no disease progression and have not died or who are lost to follow-up at the time of analysis will be censored at the date of last tumor assessment where no progression was documented or the last date of follow-up for disease, whichever is last;

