3.2 EFFECTIVENESS ANALYSIS

Effectiveness analysis population includes all patients who are enrolled and have received at least two cycles of Obinutuzumab.

In general, the time to endpoint will be defined as an interval between the date of enrolment (date of first visit) and date of first occurrence of the event. For patients who are event free, the censoring time will be calculated as a time interval between date of enrolment and the patient's final contact with available data concerning the event. The estimates and graphical presentation will be performed via Kaplan-Meier approach.

Logistic regression will be performed on the rate of endpoints in order to test the impact of covariates, i.e. age, sex, ECOG PS, Ann Arbor staging, FLIPI, hepatitis infection

(history of past/ resolved infection or latent HBV after prophylaxis as per standard treatment guidelines), chemotherapy backbone choice, medical history and history of FL, comorbidities.

Exploratory analysis between different medical treatments given or subgroup analysis will be performed using Cox regression model and including relevant covariates.

Corresponding 95% confidence intervals (CIs) will be provided for all statistical estimates.

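### SAP 3.5 will assess whether late maintenance doses affect PFS/POD24 but never says when a patient becomes delayed; a plain delayed/not-delayed split would carry immortal-time bias

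*SAP*

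**What the plan says.** SAP 3.5, under use of obinutuzumab in the real-world setting, lists as a condition of interest "administration of obinutuzumab in an interval superior to 10 days from the expected date", the expected interval being two months. A note adds: "An analysis will be performed to assess if this condition will have impact on efficacy parameters (PFS/ POD24", and says the reason for delay (COVID-19 or other) will be explored. Protocol 6.7.3 carries the same note. SAP 3.5 opens with "All exploratory endpoints will be analyzed using descriptive statistics only".

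Neither document gives this item comparison groups, a model, a time origin or a date on which a patient becomes delayed.

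The surrounding definitions are:

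- POD24 (SAP 2.3) is "defined as the time from the date of treatment initiation with Obinutuzumab until the first documented progression of disease", within 24 months. PFS (SAP 2.4.1) is "defined as the time from the date of treatment initiation until the first documented progression of disease measured by routine clinical care", or death.
- SAP 3.2 sets a different general origin: "the time to endpoint will be defined as an interval between the date of enrolment (date of first visit". Neither origin is the date on which a delay arises.
- SAP 2.1 describes about 6 months of induction, then "a maintenance treatment period (approximately 24 months) in which patients will receive Obinutuzumab monotherapy".
- The Protocol Synopsis (Table 1) gives maintenance as "Every 2 months for 2 years or until disease progression (what occurs earlier".
- SAP 3.4 plans no sensitivity analyses.

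**The concern.** Asking whether late dosing has an impact on PFS or POD24 is asking about an effect. Delay status is acquired during follow-up, and only by patients who are still progression-free and on maintenance. If patients are sorted by whether they were ever delayed and their PFS or POD24 is compared, two things happen:

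- Early progressors land in the not-delayed group by construction. The event-free time that delayed patients needed in order to become delayed is credited to delay.
- Some delays occur after month 24. They cannot have caused a POD24 event, yet they move low-risk patients into the delayed group.

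The artefact makes late dosing look harmless or protective. COVID-related maintenance delay is a named interest of the study, so this table is likely to be read.

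**Working it through.** **Plan's own figures.** The documents give no figure for the delay analysis. The sample-size figures reproduce: 39/300 gives an exact 95% CI of 9.4 to 17.3 (width 7.93), and 240/300 gives 75.0 to 84.4 (width 9.36).

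**Inputs from the documents (Protocol 6.7.5).** 300 patients; expected POD24 13%; PFS 90% at 2 years and 80% at 3 years. POD24 of 13% and 2-year PFS of 90% imply different curves, so both are used: month-24 PFS of 90%, or of 87% (the 13% anchor). Follow-up is 42 months.

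**Assumptions.** Twelve two-monthly doses are due at months 8, 10, ..., 30. Each dose has a 3%, 5%, 10% or 20% chance of being late. Delay has no effect and is unrelated to prognosis. Only patients progression-free at month 8 are analysed.

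**Step 1: schedule.** Doses due at months 26, 28 and 30, 3 of 12, fall after month 24. With independent delays, 28%, 25%, 19% and 10% of first delays (in order of rate) fall after month 24.

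**Step 2: PFS curve.** Monthly hazard h1 = -ln(S24)/24 up to month 24, then h2 = -ln(0.80/S24)/12.

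- 90% anchor: h1 = 0.00439, h2 = 0.00981. S(8) = 0.966 and S(42) = 0.754, so 300 x (0.966 - 0.754) is about 63 PFS events after month 8.
- 13% anchor: h1 = 0.00580, h2 = 0.00699. S(8) = 0.955 and S(42) = 0.767, giving about 56 events.

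With no effect of delay, POD24 from month 8 should be equal in both groups: 1 - 0.90/0.966 = 6.8%, or 1 - 0.87/0.955 = 8.9%.

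**Step 3: null ever/never hazard ratio, by simulation.** Clustering is modelled with a beta-distributed delay probability per patient at the same mean rate. The two values are for beta a+b = 2 and 1. Those runs used 60,000 patients, so the second decimal is approximate.

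| Delay per dose | Independent, 90% anchor | Independent, 13% anchor | Clustered, 90% anchor | Clustered, 13% anchor |
|---|---|---|---|---|
| 3% | 0.71 | 0.62 | not run | not run |
| 5% | 0.67 | 0.59 | about 0.8 | not run |
| 10% | 0.56 | 0.47 | 0.81, 0.87 | 0.77, 0.82 |
| 20% | 0.32 | 0.25 | 0.75, 0.84 | 0.68, 0.78 |

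A second run under independence gave 0.72 to 0.34 and 0.65 to 0.25. Starting maintenance at month 6 or 10 changes the independent values little (0.73-0.34 and 0.69-0.31, 90% anchor). Time-updated delay status gives 0.99-1.01.

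**Step 4: null POD24, delayed versus not delayed.** Independent delays at 5%: 3.0% versus 9.6% (90% anchor) and 3.9% versus 12.8% (13% anchor). Clustered delays at 10% (90% anchor): about 4.6% versus 8.0%. Under the null both groups should show the Step 2 value.

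**Step 5: does restriction to maintenance cure it?** In a separate constant-hazard run at 5% delay, null POD24 was 3.9% versus 19.3% in all patients and 3.9% versus 12.6% in those reaching maintenance. The gap narrows but stays.

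**Step 6: visibility in 300 patients.** With independent delays, the null ever/never 95% CI excludes 1 in 18%, 31%, 62% and 87% of simulated studies (90% anchor), against 4-5% for the time-updated model. With clustering at 10-20% delay, the figure is roughly 8-20%.

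**The case against.** **The split is not a stated plan.** This stands. A reader might infer that the SAP prespecifies an ever/never comparison. It does not: no groups are named, and the Appendix 3 table templates are not visible in the copy reviewed. The fault is an omission that leaves a biased analysis as the most natural descriptive reading.

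**The documents already offer tools.** Protocol 6.7.1 promises work on time-dependent confounding, and SAP 3.2 allows Cox regression with covariates. The Protocol sentence gives no method, is not tied to this item and is not repeated in SAP 3.2. A Cox model with fixed delay status has the same bias.

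**The size depends on independence between doses.** This stands. The reason the plan itself names, COVID-19, would plausibly cluster delays. Clustering moves first delays earlier and removes much of the artefact. Hazard ratios near 0.3 are the extreme end of an untested assumption.

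**Prognosis-linked delay may cancel it.** This also stands. Suppose 30% of patients have four times the hazard and four times the delay probability (base 3-10%). The crude ever/never hazard ratio is then 0.99-1.20 (13% anchor 0.81-1.04), close to the truth only because two biases offset. The time-updated hazard ratio is 0.99-1.02 when fully adjusted, about 1.5-1.7 if the factor is measured with 80% accuracy, and 1.8-2.0 unadjusted. Time-updating removes immortal time, not confounding.

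**Late consent.** Since consent may come up to a year after treatment start, a reader might infer that delayed entry at consent is required. Protocol 6.4.2 collects earlier tumour assessments retrospectively, and Protocol 6.2 does not require patients to be progression-free at consent. Delayed entry would discard observed progressions, and it changes the hazard ratio by at most about 0.002.

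**Conclusion.** The point holds as a gap in one exploratory analysis, and it should be closed before that analysis is run. A delayed/not-delayed table of PFS or POD24 is biased towards showing benefit from late dosing when there is none. The null hazard ratio is about 0.72 to 0.25 with independent delays and about 0.7-0.9 with clustered ones, at assumed rates of 3-20% per dose and maintenance from month 8. The direction is below 1 in every null scenario run with delay unrelated to prognosis; the size is not known, because the documents give no delay rate or pattern. Delay linked to poor prognosis can offset or reverse the result, so the split supports no conclusion in either direction.

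A reader might go further and infer that the study's effectiveness results are compromised. The documents do not support that: the primary POD24 and main PFS estimates do not use delay status.

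**What to change.** In SAP 3.5, exempt this item from the descriptive-only rule and state:

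1. **PFS.** Among patients who start maintenance progression-free, fit a Cox model from the start of maintenance. Delay is a time-dependent covariate that switches on the date the late dose is given, which matches the plan's own wording about administration. Adjust for a small prespecified set of collected covariates: FLIPI, age, ECOG PS and chemotherapy backbone. Switching when a dose becomes more than 10 days overdue may be added as a sensitivity analysis, listed in SAP 3.4, if reasons for held doses are recorded. Protocol 6.5.2 documents the reason for discontinuation, not for holds. If 10-30% of progressions with a dose due in the previous two months had that dose held, counting the holds as delay gives a false hazard ratio of 1.13-1.89 (90% anchor). Do not backdate the switch to the overdue date for doses known to be given later; that uses future information (null hazard ratio 0.96-0.88, 90% anchor).
2. **Ever/never tables.** PFS/POD24 by ever/never delayed may be tabulated but is not interpreted as an effect of delay. Any POD24 comparison uses a prespecified landmark and is labelled imprecise. At month 14, for example, about 282 patients are at risk with 12 later POD24 events (13% anchor: 277 and 16).
3. **Reasons.** Tabulate the reason for delay beside the estimate. State that confounding by that reason remains and can push the time-updated hazard ratio above 1.

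The cost is SAP wording and start-stop coding from dosing dates the item already needs. The downsides are wide intervals (time-updated 95% CI about a factor of 1.7-2.1 either way) and residual confounding.

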3.6 HANDLING OF MISSING DATA

There will be no missing value handling mechanisms and missing data will not be imputed.

3.7 LIMITATIONS OF THE RESEARCH METHOD

This study will be conducted in approximately 50 sites in Italy and will reflect the standard of care in place in the selected investigational study sites. Therefore, caution should be used in the generalisation of data collected in this study.

Furthermore, the design of the trial may be associated with further limitations:

- the possible bias in patients' selection due to the uncontrolled design of the trial may have impact on results;
- as when entering in the initial patient's treatment/pre-treatment data are collected retrospectively, missing data might occur in the retrospective period as well the distribution of missing data might be different across the participating investigational sites;
- pooling of prospective and retrospective data collection will be done even though not equivalent and this needs to be taken into consideration when interpreting the results;
- COVID19 pandemic may have impact on routine clinical care.

3.8 INTERIM, FINAL ANALYSES AND TIMING OF ANALYSES

An interim analysis will be performed approximately one year after the first patient is included in the study in order to evaluate safety data (particularly, infections and events COVID related), demographic data (including potentially differences in patient enrolled pre- or post- COVID19 pandemic), FLIPI, treatment choices (obinutuzumab prescription profile and chemotherapy backbone choice per Italian region, per age range, per patient's profile and site dimension - outlying sites/ universities, etc.), impact of COVID19 over maintenance delay and treatment adherence.

A second interim analysis will be performed approximately two years after the first patient included in the study in order to evaluate safety and primary, and secondary effectiveness data (including POD24), and the impact of COVID-19 on the patients management.. Tables template for second interim analysis is reported in Appendix 3.

The final analysis will be performed at the end of the study.

4. **REFERENCES**

Armitage JO. Treatment of non-Hodgkin lymphoma. *N Engl J Med* 1993; 328(14):1023-30.

Cartron G, de Guibert S, Dilhuydy MS, et al. Obinutuzumab (GA101) in relapsed/refractory chronic lymphocytic leukemia: final data from the phase 1/2 GAUGUIN study. *Blood* 2014;124:2196–202.

Izutsu K. Treatment of follicular lymphoma. *J Clin Exp Hematop* 2014;54(1):31-7.

on treatment at the time of enrollment as part of their standard procedures for treatment. In case of patients enrolled after treatment completion, these data will be collected as indicated in the Retrospective column and the prospective information will be collected as described in the Follow-up period.

^b Approximately one-year follow-up after last dose of Obinutuzumab administration, as per clinical practice, or for patients that early discontinue the treatment up to 3.5 years after first treatment administration or until withdrawal of consent, study termination by the Sponsor, or death, whichever occurs first, regardless of whether patients start a new anti-cancer therapy. For patients that discontinue treatment before completing induction or maintenance, the follow up parameters can be collected in accordance with current patient's schedule visit and not every 2 months.

^c Patients included should have performed at least 2 cycles of induction treatment with Obinutuzumab and chemotherapy, within 1 year from beginning of treatment

^d Including any medication used by the patient from 7 days prior to starting treatment with obinutuzumab.

^e Laboratory tests will include: haematology (WBCs and differential count [at least neutrophils and monocyte %], RBCs, haemoglobin, haematocrit, platelet count) and blood chemistry (creatinine, beta-2 microglobulin, LDH, AST, ALT).

^f Data collected if performed per clinical practice as clinically indicated.

^g QoL will be completed prospectively period, every 2 cycles in induction treatment phase and every 2 months during maintenance treatment phase. For further instructions over QoL completion please refer to section 6.6.1. PRO questionnaires (FACT-Lym, EQ-5D) should be administered prior to any treatment assessments. PRO questionnaires should also be administered at first assessment after report of disease progression.

^h AEs/SAEs/IRR/ADR that occur prior ICF signature should be reported in eCRF as available; however only the event preferred term as per CTCAE vs 5.0 is required as Individual Case Safety Report are not applicable. Prospective safety that must be fully assessed and reported by study physician including assessment of seriousness (see Section 8.1.1.2), severity (see Appendix 3), and causality (see Appendix 3).

ⁱ FLIPI score (age, number of nodal sites, LDH level, haemoglobin, stage) or FLIPI2 (age, beta-2 microglobulin, bone marrow involvement, longest diameter of largest involved node, haemoglobin) collected at diagnosis.

^j Response will be collected at mid of the induction (between 10 and 14 weeks after the start of treatments), end of the induction (at the day of cycle 6 until 1 month later) during maintenance (1 year after the start of treatment, i.e. from 10 to 14 months after the start of treatment; 2 years after the start of treatment, i.e. from 22 to 26 months after the start of treatment; 3 years after the start of treatment, i.e. from 34 to 38 months after the start of treatment), at the end of maintenance and at Follow-up as per clinical practice, as well as at any tumor assessment that shows disease progression, CR or CRu during induction or maintenance. The assessment of tumor response will be based on standard Cheson criteria and the Deauville 5-point scale (Appendix 6) (Younes *et al.* 2017).

^k All adverse events data available in medical records after start of the treatment should be reported until 185 days after the last obinutuzumab dose or until starting a new anti-cancer therapy (whichever occurs first). After this period AEs that are believed to be related to prior study drug treatment will be collected.

Appendix 2

List of Planned Outputs

Output for baseline descriptive analyses

- Summary of demographic characteristics
- Listing of demographic characteristics
- Summary of history of treatment with Obinutuzumab and chemotherapy
- Summary of follicular lymphoma characteristics
- Summary of clinical staging pre treatment
- Summary of FLIPI/FLIPI2 (at treatment start)
- Summary of medical history (other than FL)
- Listing of medical history (other than FL)
- Summary of physical examination
- Listing of physical examination abnormalities
- Summary of vital signs and ECOG
- Listing of vital signs and ECOG
- Summary of hematology, blood chemistry and serology
- Summary of tumor assessment and target and not target lesions
- Listing of target and not target lesions
- Summary of bone marrow evaluation

Output for effectiveness analyses

- Results regarding POD24
- Results regarding PFS
- Results regarding TTNT
- Results regarding OS
- Results regarding TTLCB
- Results regarding ORR
- Results regarding CR
- Results regarding CR30
- Results regarding duration of response
- Results regarding time to response
- Results regarding SD
- Results regarding effectiveness of Obitunuzumab in patient subgroups

Output for safety analyses

- Summary of Adverse Events and IRRs
- Listing of Adverse Event and IRRs
- Summary of clinical laboratory abnormalities during the study
- Summary of vital signs during the study

Output for exploratory analyses

- Summary of treatment pattern

- Summary regarding method applied to tumour response evaluation (e.g. FDG-PET)
- Summary about quality of life information from questionnaire
- Summary of presence of B symptoms during the study
- Summary regarding effectiveness in off-labels
- Summary regarding COVID19 impact on therapy maintenance
- Summary of concomitant medication
- Listing of concomitant medication

Appendix 3

Tables template for second interim analysis

Certificate Of Completion

Envelope Id: 91E6F38C07BF47F3875A27846F3045AE Status: Completed

Subject: Please DocuSign: StatisticaAnalysisPlan - URBAN - Vers 2 TB signed.pdf

Source Envelope:

Document Pages: 22 Signatures: 1

Certificate Pages: 4 Initials: 0

AutoNav: Enabled

Enveloped Stamping: Disabled

Time Zone: (UTC+01:00) Amsterdam, Berlin, Bern, Rome, Stockholm, Vienna

Envelope Originator:

[name]

[name]

IP Address: [REDACTED]

Record TrackingStatus: Original Holder: [REDACTED] Location: DocuSign
2/1/2022 5:48:48 PM [REDACTED]**Signer Events****Signature****Timestamp**[REDACTED]
[REDACTED]
Sent: 2/1/2022 5:50:10 PM
Viewed: 2/1/2022 5:50:59 PM
Signed: 2/1/2022 5:58:03 PM

Roche S.p.a.

Security Level: Email, Account Authentication
(Required), Login with SSO

Signature Adoption: Pre-selected Style

Signature ID:
053BD39F-A252-4544-A364-2F873F26579C
Using IP Address: [REDACTED]

With Signing Authentication via DocuSign password

With Signing Reasons (on each tab):

I approve this document

Electronic Record and Signature Disclosure:

Accepted: 9/25/2020 9:38:56 AM

ID: 196c6b45-7c21-4ab0-abea-47e4a6c71082

Company Name: F.Hoffmann-La Roche Ltd. - CFR Part 11 - Sub 1

In Person Signer Events	Signature	Timestamp
Editor Delivery Events	Status	Timestamp
Agent Delivery Events	Status	Timestamp
Intermediary Delivery Events	Status	Timestamp
Certified Delivery Events	Status	Timestamp
Carbon Copy Events	Status	Timestamp
Witness Events	Signature	Timestamp
Notary Events	Signature	Timestamp
Envelope Summary Events	Status	Timestamps
Envelope Sent	Hashed/Encrypted	2/1/2022 5:50:10 PM
Certified Delivered	Security Checked	2/1/2022 5:50:59 PM
